The RP2D will be defined in consideration of the MTD (if any), safety data, and pharmacodynamic data. The RP2D will be communicated to all sites in a trial memo following the last SMC cohort review.

Subject replacement: If a subject discontinues for any reason other than toxicity prior to completing 28 days of ELI-002 therapy, a replacement subject will be added to the cohort until 3 subjects per cohort complete 28 days of ELI-002 therapy.

DLT definition: A DLT will be defined as any event at least possibly related to ELI-002 as follows:

- a. Any Grade  $\geq 3$  non-hematologic toxicity except asymptomatic laboratory abnormalities (see Section 12.2.1.1)
- b. Any Grade  $\geq 3$  toxicity involving major organ systems for greater than 72 hours and occurring within 28 days of subcutaneous administration
- c. Grade 3 CRS that does not resolve to  $\leq$  Grade 2 within 7 days
- d. Any Grade 4 CRS that does not improve to  $<$  Grade 2 within 72 hours
- e. Any Grade  $\geq 3$  autoimmune disorder
- f. Any Grade  $\geq 3$  rash that does not resolve to  $\leq$  Grade 1 within 7 days with appropriate treatment

The DLT observation period will be 28 days.

MTD definition: The MTD is defined as the highest dose level with a DLT incidence  $<33\%$  of cohort subjects.

The trial will consist of a Screening Period, an Immunization Period, a No Dosing 3-Month Period, a Booster Period, and a Follow-up Period.

A Booster Period is provided as further lymph node antigen exposure may be required to maintain effective levels of antigen-specific T-cells. All subjects will receive booster doses unless they have unresolved toxicity.

All subjects will be observed for safety and tolerability. CT imaging with contrast will occur at screening and 35 days post first dose and at additional timepoints until radiographic relapse is observed.

The central laboratory will confirm  $\geq 1$  of 2 mutant KRAS/NRAS alleles targeted by ELI-002 Amph-Peptides 2P (G12D, and G12R,) is present and central laboratory ctDNA must be positive or there must be serum tumor biomarker (such as CA19-9, CEA, and CA-125) elevation at  $\geq 21$  days post-surgery or after last administration of adjuvant therapy (whichever comes last in the specific subject treatment plan). These data are required for determination of eligibility and inclusion into the trial.

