- Cohort 3 Dose Level 3: Amph-CpG-7909 2.5 mg with Amph-Peptides

Phase 1 cohorts will consist of 3 to 6 subjects (the number will depend on whether DLTs are observed). In order to ensure an adequate number of evaluable subjects, up to 6 subjects may be enrolled per cohort even in the absence of a DLT. Once the RP2D is determined, the cohort evaluating the RP2D will be expanded as needed so that there is safety experience with at least 6 subjects at this dose level.

Dose escalation from one cohort to the next will be determined by the SMC, and will be based on treatment-emergent AEs, clinical laboratory data, PE findings including vital signs, after all subjects within a cohort have completed 28 days. At each SMC meeting, longer follow-up will

be available on all but the final subject in each cohort. The SMC will review all available long-term safety information from prior cohorts (if any), so that the SMC will consider the totality of the safety information in their recommendation.

The trial will consist of:

- A Screening Period in which study specific procedures, including eligibility determination, will begin at Visit 1, following surgical resection.
- An Immunization Period which will consist of 6 SC injections: 4 weekly injections (Visit 3 to Visit 6) followed by 2 injections every two weeks at Visit 7 and Visit 8.
- A No Dosing 3-Month Period in which subjects will continue to be observed and evaluated.
- A Booster Period, consisting of 4 weekly injections (Visit 12 to Visit 15), in which eligible subjects will receive further lymph node antigen exposure.
- A Follow-up Period which will provide continued safety and efficacy data.

All subjects will be observed for safety and tolerability. Computed tomography (CT) with contrast or magnetic resonance (MRI) imaging will occur at screening and at additional timepoints indicated in the Schedule of Assessments, [Table 13](#) and [Table 15](#), until confirmed radiographic relapse is observed.

The central laboratory will confirm that at least 1 of the 2 mKRAS/NRAS alleles targeted by ELI-002 2P (G12D and G12R) is present and either ctDNA is positive or there are successive rising values of serum biomarker (such as CA19-9, CEA, or CA-125) from samples taken at  $\geq 21$  days post-surgery or after the last administration of adjuvant treatment (whichever comes last in the specific subject treatment plan). These data are required for determination of eligibility and inclusion into the trial.

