#### **13.3.3. Efficacy Analysis**

##### **13.3.3.1. Relapse-free survival**

Relapse-free survival will be censored on the date of the last evaluable CT scan on trial for subjects who do not have recurrence and who do not die while on trial. Subjects without any post baseline CT scans will have their RFS time censored on the date of randomization. Subjects who withdraw from the trial (including withdrawal of consent and lost to follow-up) will be censored at the last of the last CT scan. For disease recurrence documented by CT between scheduled evaluations, the actual date of the scan will be used. For death or recurrence after no more than

1 missed evaluation, the date of the event will be the date of recurrence or death, whichever occurs first. For death or recurrence after more than 1 missed evaluation, RFS will be censored at the last evaluable disease assessment.

RFS (in months) is calculated as:

- $[(\text{date of recurrence/death} - \text{date of randomization}) + 1]/30.4375$

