**Table 16: Censoring Rules for RFS, 1-Year RFS and OS**

**Final Analysis  
Statistical Analysis Plan (SAP)**

Situation	Event or censored date	Event or Censored
Censoring Rules for RFS/Primary Analysis		

No subsequent anti-cancer therapy initiated or lost to follow up/withdrawal of consent for follow up:                      Death or recurrence (iCPD)
 
No recurrence or death
	
Date of recurrence (iCPD) or death, whichever occurs first
 
Date of last evaluation CT/MRI visit, without documentation of recurrence of disease (iUPD or absence of progression)
	
Event
 
Censor

Subsequent anti-cancer therapies initiated:                      Death or recurrence (iCPD) after no more than 1 consecutive missed CT/MRI evaluation (ie, <math>\leq 182</math> days (24 weeks + 2 weeks) after start of subsequent anti-cancer therapies
 
No recurrence or death after no more than 1 consecutive missed CT/MRI evaluation (ie, <math>\leq 182</math> days (<math>\leq 24</math> weeks + 2 weeks) after start of subsequent anti-cancer therapy
	
Date of recurrence (iCPD) or death, whichever occurs first, according to the following:                      If death occurs without recurrence, then event is the date of death                      If recurrence occurs prior to death, then the date of last evaluable CT/ MRI visit, without documentation of recurrence of disease (iUPD or absence of progression), that is done before the start of subsequent anti-cancer therapy
 
Date of last evaluable CT/ MRI visit, without documentation of recurrence of disease (iUPD or absence of progression), that is done before the start of subsequent anti-cancer therapy
	
Event
 
Censored

Incomplete or no baseline assessment	Date of start of treatment (censored on Day 1)	Censored
No post baseline CT/MRI scans	Date of start of treatment (censored on Day 1)	Censored
Treatment discontinuation for undocumented progression or for toxicity	Date of last evaluation CT/MRI visit, without documentation of recurrence of disease ( iUPD or absence of progression)	Censored
Censoring Rules for RFS/Secondary Analysis		

**Final Analysis  
Statistical Analysis Plan (SAP)**

Situation	Event or censored date	Event or Censored

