### 13.6.2 Analysis of Median RFS

Relapse-free survival (RFS), defined as time from first dose of ELI-002 2P until recurrence/ death. RFS (in months) is calculated as:

$$[(\text{date of recurrence/death} - \text{date of first ELI-002 dose2P dose}) + 1]/30.4375$$

Censoring details are described in Table .

Median RFS will be estimated using the Kaplan-Meier method. Number of subjects with events (recurrence/death) and number of subjects censored and reason of censoring will be presented along with an estimate for median time (days), Q1, and Q3. A Kaplan-Meier plot for time to event will also be provided by cohort. Tables and figures will be created for each of the two censoring rules presented in Table 16 for RFS.

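### Both RFS analyses censor an unconfirmed radiographic relapse (iUPD) that is followed by new anti-cancer therapy, unless death or confirmed progression follows; this likely biases RFS upward, and no planned analysis tests it

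*SAP*

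**What the plan says.** SAP Section 13.6.2 has RFS "defined as time from first dose of ELI-002 2P until recurrence/ death" and reports tables and figures under both rule sets of Table 16.

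**Primary rules, new therapy started.**
- If neither death nor iCPD occurs within 182 days of the new therapy, the subject is censored at the "date of last evaluable CT/ MRI visit, without documentation of recurrence of disease". Table 16 explains that status as "iUPD or absence of progression" and restricts the scan to one "that is done before the start of subsequent anti-cancer therapy".
- For death inside the window: "If death occurs without recurrence, then event is the date of death".
- iCPD inside the window is also labelled an event. The date attached to it is that of the last scan without recurrence, a separate matter that needs clarifying.

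**Secondary rules, new therapy started.** iUPD has the same status and death is again an event. There is no 182-day figure, and the censoring scan need not precede the new therapy.

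**Protocol Section 13.3.3.1.** "For disease recurrence documented by CT between scheduled evaluations, the actual date of the scan will be used". This section does not name iCPD and has no censoring for new therapy. SAP Section 14, which lists changes from the protocol, does not mention the new-therapy censoring. The SAP revision history names RFS windows and censoring rules as changed, without saying what changed.

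**When scanning stops.** The protocol synopsis has CT "at additional timepoints until radiographic relapse is observed"; Section 6.1 has imaging "until confirmed radiographic relapse is observed".

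**The concern.** Kaplan-Meier treats a censored subject as having the same future risk as those still under observation. A subject whose scan shows possible new disease, and who is then moved to other therapy, probably does not. If the subject is censored at that scan, the finding leaves the analysis just when it carries most information.

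The setting makes unconfirmed iUPD plausible. No dedicated confirmation scan is scheduled, and after the first post-dose scan the routine scans are 56 to 140 days apart.

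The quantities affected are the descriptive median RFS, 1-year RFS and the planned correlation of biomarkers with RFS. All are exploratory, but they have a purpose. SAP Section 13.1 says the efficacy summaries are to inform later studies, and protocol Section 4.6.5 looks to RFS when pivotal trials are designed. RFS would look better the more often subjects were switched before confirmation.

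**Working it through.** The documents give no event count or power for RFS, so the only figure to reproduce is the window: 24 × 7 + 14 = 182 days, which agrees.

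**Step 1: follow one subject through the primary rules.** The subject has iUPD at scan A and starts new therapy before another scan.
- Dies within 182 days of the new therapy with no iCPD: event, dated at death, so later than scan A.
- iCPD within 182 days: labelled an event.
- Neither: censored at scan A, because Table 16 counts iUPD as a scan without documented recurrence.

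The secondary rules also leave unconfirmed iUPD as a non-event. No planned analysis makes it an event.

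**Step 2: a hand example with 18 subjects.** Suppose 10 have iUPD at the first post-dose scan and k of them are censored there. The Kaplan-Meier estimate just after that scan is 1 − (10 − k)/18:
- k = 0: 0.444
- k = 2: 0.556
- k = 4: 0.667
- k = 6: 0.778

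**Step 3: an illustration on the protocol's scan days (primary rules).**

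Inputs from the documents:
- CT on Days 148, 259, 399, 483, then every 84 days to 1071, and 1127, with first dose on Day 57. This gives scans 91, 202, 342, 426, … 1070 days after first dose.
- The 182-day window.
- A 5-month median RFS for ctDNA-positive resected pancreatic cancer (protocol Section 4.6.4), used as the shorter relapse time.

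Assumptions not in the documents:
- Exponential relapse with median 5 or 10 months, and every iUPD a true relapse.
- New therapy 14 days after iUPD.
- Exponential survival after iUPD with median 6 or 12 months.
- A share q of iUPD subjects treated without confirmation.
- All other relapses count at the iUPD scan in both analyses, so only the unconfirmed ones differ.

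If every iUPD is an event, 1-year RFS is the chance of no relapse by the day-342 scan, 2^(−342/(30.4375 × m)). This is 21% for m = 5 and 46% for m = 10.

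The share of unconfirmed subjects who still enter as deaths is 1 − 2^(−196/(30.4375 × d)), where 196 = 14 + 182. This is 52% for d = 6 and 31% for d = 12.

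Simulated 1-year RFS under Table 16, with ranges over the two survival medians (Monte Carlo error about 1 point):

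| Median relapse time | iUPD always an event | q = 10% | q = 25% | q = 50% | q = 75% |
|---|---|---|---|---|---|
| 5 months | 21% | 23–25% | 29–31% | 38–42% | 46–55% |
| 10 months | 46% | 49% | 53–55% | 61–64% | 69–74% |

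For q from 25% to 75%, the rise runs from 53 − 46 = 7 to 55 − 21 = 34 points. Median RFS moves from 6.6 to about 7–14 months, and from 11.2 to about 14–23 months.

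For scale, the binomial standard error with 18 subjects is √(0.21 × 0.79/18) = 0.096, or about 10 points, and √(0.46 × 0.54/18) = 0.117, or about 12 points.

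**The case against.** A reader might infer that these relapses never enter RFS. Table 16 does not support that, because death or iCPD inside the window is an event. Censoring all such subjects would overstate the effect: at q = 50% and a 5-month median it gives a 1-year RFS of 51%, against 38% to 42% under the rules as written.

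A reader might also infer that confirmation becomes impossible once new therapy starts. It does not. Table 16 has a branch for iCPD after new therapy, and subjects who stop treatment are meant to stay in follow-up with CT. Unscheduled imaging is allowed on clinical signs of progression, and a standard-of-care biopsy may confirm progression. These routes reduce the number affected. They are optional or depend on circumstances, so they do not remove the mechanism.

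Nor does requiring confirmation by itself contradict the protocol. The synopsis and Section 11 assess RFS by iRECIST. Section 6.1.2 reports that pseudoprogression has been seen in this trial, which is a good reason not to equate every iUPD with relapse. The departure that does stand is narrower: the new-therapy censoring is absent from protocol Section 13.3.3.1 and is not declared in SAP Section 14.

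The synopsis wording on when scanning stops may be only a summary that dropped a word; the synopsis itself uses confirmed relapse elsewhere. It is an inconsistency to tidy, not evidence that scans were lost.

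Finally, RFS is exploratory in about 18 subjects, and no dose decision or primary endpoint rests on it. That limits the stakes but does not make the estimate unbiased.

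**Conclusion.** The concern holds in this form. In both RFS analyses, iUPD followed by new therapy without confirmation is censored unless death or iCPD follows (primary analysis: within 182 days of the new therapy). The censoring is plausibly informative and likely pushes median and 1-year RFS upward. No planned analysis shows by how much.

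The direction rests on new therapy after iUPD being related to true relapse. The size cannot be stated. The illustrative 7 to 34 points assume that 25% to 75% of iUPD subjects are treated unconfirmed and that no iUPD is pseudoprogression, so they lean high. At 10% the rise is 2 to 4 points, well under one standard error. The illustration covers the primary rules only. This should be corrected, but it does not affect the trial's safety conclusions.

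**What to change.** 1. Add one RFS analysis, with a table and a Kaplan-Meier plot, to Table 16: iUPD followed by subsequent anti-cancer therapy, with no intervening scan showing resolution, is an event at the date of the iUPD scan. Report it beside the two existing rule sets.
2. Do not count iUPD followed only by the absence of another scan as an event. Long-term follow-up was ended early, so such a rule would turn some administrative endings into relapses.
3. List the new-therapy censoring in SAP Section 14 as a change from protocol Section 13.3.3.1.
4. Reconcile the protocol synopsis with Section 6.1 on when scanning stops.

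The cost is a few lines of SAP text, one table and one plot. The downside is that an occasional pseudoprogression treated early will count as a relapse in the added analysis, which is why it should stand beside the current rules and not replace them.

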### 13.6.2 Analysis of Median RFS

Relapse-free survival (RFS), defined as time from first dose of ELI-002 2P until recurrence/ death. RFS (in months) is calculated as:

$$[(\text{date of recurrence/death} - \text{date of first ELI-002 dose2P dose}) + 1]/30.4375$$

Censoring details are described in Table .

Median RFS will be estimated using the Kaplan-Meier method. Number of subjects with events (recurrence/death) and number of subjects censored and reason of censoring will be presented along with an estimate for median time (days), Q1, and Q3. A Kaplan-Meier plot for time to event will also be provided by cohort. Tables and figures will be created for each of the two censoring rules presented in Table 16 for RFS.

### 13.6.3 Analysis of Overall Survival (OS)

The OS (in months) is defined as time from first dose of ELI-002 2P until death from any cause.

$$[(\text{date of death or last known alive} - \text{date of first ELI-002 2P dose}) + 1]/30.4375$$

Subjects who are lost to follow-up or do not have a date of death at the time of data cut-off will be censored at the last date that they were known to be alive. Censoring details are described in Table 16.

Median OS will be estimated using the Kaplan-Meier method. The number of subjects with events (recurrence / death) and number of subjects censored and reason of censoring will be presented along with estimate for Q1, Q2 along with median time (days). Kaplan-Meier plot for time to event will also be provided by cohort in each phase.

## 13.7 Safety Analyses

All summaries of safety data will be conducted for the safety analysis set using actual treatment received. Safety measurements will include

- Adverse Event (AEs)
- Clinical laboratory evaluations
- Vital sign measurement
- Physical examinations
- 12-lead ECG
- ECOG performance status.

No statistical test will be performed on these safety endpoints above.

### 13.7.1 Adverse events

All Adverse events (AEs) will be classified by Primary System Organ Class (SOC) and Preferred Term (PT) according to the Medical Dictionary for Regulatory Activities (MedDRA) Version 23.1 or higher.

**Final Analysis  
Statistical Analysis Plan (SAP)**

AEs will be graded according to the National Cancer Institute Common Terminology Criteria for Adverse Events (NCI CTCAE) version 5.0. For CRS/ICANs (Immune effector Cell-Associated Neurotoxicity syndrome), AEs will be graded according to the American Society for Transplantation and Cellular Therapy (ASTCT) criteria.

In summaries by SOC and PT, the SOC terms will be presented alphabetically, and PTs within each SOC will be sorted by decreasing frequency within the overall column. In summaries by PT, AEs will be sorted by decreasing frequency in the overall column.

**TEAE:** any events not present prior to the initiation of study treatment or any event already present that worsens in either intensity or frequency following exposure to study treatment. Details for imputing missing or partial start dates of adverse events are described in Section 7.3.1.

AE summary tables will be presented for the following categories using counts and percentage of subjects (i.e., number and percentage of subjects with an event):

**Table 7: Planned Summaries of Adverse Events**

AE Type \ Summarize by	Overall Summary [*]	By Cohort and Overall, SOC & PT	Additional Summary
TEAEs	X	X	By Cohort and Overall/Maximum CTCAE grade/SOC/PT By Cohort and Overall leading to study discontinuation
Serious TEAEs	X	X	By Cohort and Overall/relationship to study treatment/SOC/PT
Leading to study treatment discontinuation	X	X	By Cohort and Overall/relationship to study treatment/SOC/PT By Cohort and Overall/PT
Leading to death	X	X	
DLT (Phase 1A only) [#]	X	X	
Related TEAE	X	X	By Cohort and Overall/ leading to study discontinuation
Related TEAEs leading to study treatment discontinuation	X	X	
Cytokine Release Syndrome	X	X	
ICANS		X	
Reactogenicity event	X		By Reactogenicity type, events and toxicity grade

Note: all summary tables will be by Phase, Cohort/Overall.

**Final Analysis  
Statistical Analysis Plan (SAP)**

[\*] All types of AEs with “X” sign will be summarized in one overall summary table of TEAE, including outcome and action taken.

[#] Dose Limiting Toxicities (DLTs) are defined in the Protocol Section 6.7.3. The percentage of subjects having a DLT is based on all treated subjects in each cohort. DLT flag may be added to selected listings of adverse events as appropriate.

Where a subject has the same adverse event, based on PT reported multiple times, the subject will only be counted once at that PT level. Where a subject has multiple adverse events within the same system organ class, the subject will only be counted once at that SOC level.

Any AE with a missing severity based on CTCAE grading, or ASTCT in the case of CRS or ICANS, will be presented in the summary table under the category of “Missing” and will not be imputed. Any AE with a missing relationship to study treatment will be imputed as “Related”. Any AE with a missing “Serious” evaluation will be imputed as “Serious”.

For all AE data captured in the study by the Case Report Form (CRF), by-subject listings will be provided for all AEs, serious TEAEs, TEAEs leading to dose reduction or interruption, DLT and death, respectively.

Cytokine Release Syndrome, ICANS, and reactogenicity to the vaccine data captured in the CRF will be provided in a by-subject listing.

### **13.7.2 Clinical laboratory evaluations**

Laboratory assessments comprise safety laboratory tests (hematology, blood chemistry and coagulation), serum cytokines, pregnancy and viral laboratory screening tests. For the purposes of summarization in both tables and listings, all laboratory values will be presented in SI units. If a lab value is reported using a nonnumeric qualifier e.g., less than (<) a certain value, or greater than (>) a certain value, the given numeric value will be used in the summary statistics, ignoring the nonnumeric qualifier.

Laboratory test results and change from baseline of serum cytokine, worst on treatment hematology and chemistry results will be summarized using descriptive statistics by cohort/dose level, scheduled, and unscheduled visits.

For all clinical laboratory result listed in the protocol and captured by the CRF, by-subject, by-visit listings will be provided and abnormal flags (low or high) will be provided.

